Accordingly, the demand for next-generation P2Y12 antagonists has continued, and according to a paper published in 2007, clopidogrel and prasugrel patient responses and platelet activity inhibition were compared before percutaneous coronary intervention [1]. Reportedly, the platelet aggregation inhibitory effect is remarkably high. Choi et al. revealed the efficacy of prasugrel in coil embolization of cerebral aneurysms with stent insertion; the incidence of thromboembolism was significantly lower in the prasugrel group than in the clopidogrel group (0.9% vs. 6.4%; $P = 0.01$), and the bleeding risk was reported to be similar (0.5% vs. 2.2%; $P = 0.22$) [2,3]. However, these recent studies are based on single-center retrospective data; therefore, there is a limit to the level of evidence.

This study aimed to compare the safety and usefulness of prasugrel vs. clopidogrel in patients scheduled to undergo stent or diverter treatment for unruptured cerebral aneurysms.

Specific Aim and Hypothesis

The primary aim of the present study was to investigate the effect of prasugrel in patients undergoing neurointerventional treatment for UIAs (i.e., stent-assisted coiling or flow diverter insertion). The prasugrel and clopidogrel groups were compared to elucidate their safety (hemorrhagic complications) and efficacy (thromboembolic complications) in the periprocedural period. In the present study, we hypothesized that prasugrel has a preventive effect that is not inferior to that of clopidogrel in any treatment group.

Research Design and Methods

Research Design

Patients who visited the outpatient department of neurosurgery at multiple institutions (Severance Hospital, Gangnam Severance Hospital, Yongin Severance Hospital, Ewha Womans University Seoul Hospital, Bucheon St. Mary's Hospital, and International St. Mary's Hospital) were screened to participate in the present research. After following the study protocol, the participants were divided into the prasugrel and clopidogrel groups by 1:1 randomization.

- Detailed information of the study protocol
- 1) After patients with UIAs were hospitalized, baseline characteristics were obtained, and blood tests, including renal function test (glomerular filtration rate [GFR]), liver function test (aspartate aminotransferase [AST]/alanine aminotransferase [ALT]), and pregnancy test, were performed.
- 2) Cerebral angiography was performed, and detailed consent was obtained after the study protocol was explained to the participants who met the selection criteria.
- 3) Using a randomization program, the test group (203 patients; aspirin 100 mg + prasugrel 5 mg) and the control group (203 patients; aspirin 100 mg + clopidogrel 75 mg) were classified.
- 4) The above drugs were prescribed according to the assigned group and taken 5 days before the procedure.
- 5) The patients were hospitalized 2 days before the procedure, and whether the drug was taken was checked immediately after hospitalization (if the drug was not taken properly, the patient was excluded from the study).

6) The platelet function test (VerifyNow assay; Accumetrics, San Diego, California, USA) was performed a day before the procedure to check the clopidogrel responsibility and adjust the drug according to the result.

P2Y12 reaction units (PRU) <220

- Clopidogrel group: aspirin 100 mg + clopidogrel 75 mg
- Prasugrel group: aspirin 100 mg + prasugrel 5 mg

PRU ≥220

- Clopidogrel group: aspirin 100 mg + clopidogrel 75 mg + cilostazol 100 mg
- Prasugrel group: aspirin 100 mg + prasugrel 5 mg + prasugrel 5 mg

The morning on the day of the procedure, after administering the drug at the adjusted dose, the planned intracerebrovascular procedure was performed.

7) Brain magnetic resonance imaging (MRI) was performed within 7 days from the day of the procedure (i.e., from the day of the procedure to 1 week after the procedure, and it varied depending on the clinical situation).

8) If there were no neurological abnormalities or complications, the patient was discharged with discharge medication on the next day following the procedure.

- Clopidogrel group: aspirin 100 mg + clopidogrel 75 mg
- Prasugrel group: aspirin 100 mg + prasugrel 5 mg

9) On postoperative day 30 (30-35 days after the procedure), the patient's clinical courses and complications were assessed. If there were no specific findings, the drug was changed to aspirin 100 mg + clopidogrel 75 mg in both groups.

- Time table

Procedure	Screening	Pre-medication	Admission	Medication adjustment	Treatment	Follow-up 1 (MR)	Follow-up 2	Follow-up 3
Time period	Day -60 ~ -6	Day -5 (out-patient)	Day -2 (in-patient)	Day -1 (in-patient)	Day 0 (in-patient)	Day 1 (in-patient)	Day 2 (discharge)	Day 30
Visit window	-	0~± 1 day	0~± 1 day	0 ~+1 day	-	0~+1 day	0~+3 days	0~± 5 days
Informed consent	O	-						
Inclusion/Exclusion Criteria	O	-						
Demographic data	O	-	O					
Medical History	O	-	O					
Vital sign	O	-	O		O	O	O	O
Neurological examination	O	-	O		O	O	O	O
Aneurysm data	O	-						
Radiologic data	O	-			O	O		
Medication compliance	-	-	O					O
VerifyNow test	-	-	-	O				

Study Population

At the time of initial admission for pretreatment examination, patients were screened based on their medical history, vital sign evaluation, and laboratory tests (hematological tests, biochemical tests, urinalysis, and pregnancy test). Detailed inclusion and exclusion criteria of the present study were as follows:

- **Inclusion Criteria**

- Patients aged between 19 and 75 years
- Aneurysms without any evidence of rupture on an intracranial imaging study within the last 6 months
- Planned treatment with coil embolization with stent insertion or flow diverter insertion
- If the patient itself consented to this study

● **Exclusion Criteria**

- History of acute ischemic stroke or transient ischemic attack
- Any intracranial hemorrhage except subarachnoid hemorrhage due to aneurysm rupture within the last 3 months
- Concurrent treatment other than endovascular procedures (e.g., open craniotomy and microsurgical clipping)
- Contraindications to iodine contrast agents
- Already taking antiplatelet or antithrombotic drugs other than aspirin
- Hypersensitivity to aspirin, prasugrel, or clopidogrel
- Cardiac arrhythmia that should be needed to take anticoagulants
- Pregnant or lactating women
- Chronic kidney disease (GFR <60)
- Patients with chronic liver disease who had at least 100 IU/L of either AST/ALT in the liver function test
- Patients with pathological active bleeding, as seen in peptic ulcer
- Patients with genetic problems such as galactose intolerance, Lapp lactase deficiency, or glucose-galactose malabsorption because they contain lactose
- Patients continuously taking non-steroidal anti-inflammatory drugs and cyclooxygenase-2 inhibitors
- Patients requiring concomitant administration of ≥ 15 mg methotrexate for a week
- If the case was difficult to follow up after treatment

Randomization

Randomization was conducted using the randomization program provided by the Seoul National University Hospital Biomedical Research Institute (<http://mrcc.snu.ac.kr>) and managed by a third party to ensure that the researchers were blinded to the assignments.

Study Endpoints

The primary endpoint was intraprocedural thromboembolic complications or

postprocedural ischemic stroke or death. The detailed information is as follows:

- A thromboembolism detected during the neurointerventional procedure
- Transient ischemic attack, ischemic stroke, or death with evidence of infarction on diffusion-weighted imaging, occurring within 30 days after the procedure

The secondary endpoints were postprocedural stroke and diffusion-restricted lesions on diffusion-weighted MRI. Another secondary endpoint was the preprocedural platelet function test value and its adjustment ratio. The details are as follows:

- Ischemic stroke in the relevant arterial territory within 30 days after the procedure
- Any stroke, including ischemic and hemorrhagic strokes, within 30 days after the procedure
- Disabling or fatal stroke within 30 days after the procedure
- Diffusion-restricted lesion detected on the 7-day postprocedural MRI

The safety endpoints were bleeding related to P2Y12 antagonists, including any bleeding within 30 days or major bleeding. Bleeding criteria followed the PLATelet inhibition and patient Outcomes bleeding criteria [4,5].

- Major bleeding criteria
 - ✓ Fatal bleeding (bleeding that directly results in death within 7 days)
 - ✓ Intracranial bleeding
 - ✓ Intrapericardial bleeding with cardiac tamponade
 - ✓ Hypovolemic shock or severe hypotension due to bleeding, requiring pressors or surgery
 - ✓ A decline in the hemoglobin level of ≥ 5.0 g/dL
 - ✓ Need for transfusion of at least 4 units of red blood cells
- Other major bleeding criteria
 - ✓ Bleeding that led to clinically significant disability
 - ✓ Decline in hemoglobin level of ≥ 3.0 g/dL but < 5.0 g/dL
 - ✓ Need for transfusion of at least 2-3 units of red blood cells
- Minor bleeding criteria
 - ✓ Any bleeding requiring medical intervention but not meeting the criteria for major bleeding

Determination of the Sample Size

Given the hypothesis of the present study, we used a two-proportion Z-test with pooled variance and set the significance level at 0.05, power = 0.8.

In previous retrospective studies, intraprocedural thromboembolism occurred in the prasugrel group (0.009) and the clopidogrel group (0.064), with a -0.055 difference in the ratio of any stroke and death during the 30-day treatment. A total of 182 samples were required to prove significance at 80% for each group. Considering the 10% dropout rate, 203 patients were required per group, with a total of 406 patients.

Statistical Analysis

Statistical analysis was performed using SAS®(25) version 9.4 or later versions. All the efficacy analyses were based on the intention-to-treat principle. For comparison of all study endpoints (primary, secondary, and safety), 1) ratio data were analyzed using Pearson's chi-square test and 2) continuous variable comparison was analyzed using an independent two-sample t-test. All statistical tests were based on a two-tailed test with a significance level of 5%, and the safety analysis presented observations without correction for missing values.

- Baseline characteristics

Continuous variables are expressed as the mean \pm standard deviation. Categorical and continuous variables of the baseline characteristics were compared and analyzed using the chi-square or Fisher's exact test and Student's t-test.

- All endpoints

For comparison of all endpoints (primary, secondary, and safety) in the two groups, 1) ratio-type data were analyzed using Pearson's chi-square test and 2) continuous variable comparison was analyzed using an independent two-sample t-test. Statistical significance was set at $P < 0.05$.

- Exploratory subgroup analyses

For the following pre-defined subgroups, subgroup analysis was performed to determine the difference between the overall primary and secondary endpoints.

- ✓ Previous major cardio-cerebrovascular accident
- ✓ Clopidogrel responsiveness (hyporesponder, $PRU \geq 220$; responder, $PRU < 220$)

- ✓ Cerebral aneurysm size in the stent group (<5 mm or \geq 5 mm)
- ✓ Parent artery diameter (mean diameter <2.5 mm or ≥2.5 mm)
- ✓ Procedure (stent-assisted coiling, flow-diverter)
- ✓ Occlusion grade (Roy-Raymond classification)

The difference between the test and control groups according to subgroup followed the regression model with interaction.

Possible Risks and Benefits

Prasugrel and clopidogrel are widely used for treating cardiovascular diseases, and clopidogrel is the standard treatment for cerebrovascular diseases. In the case of prasugrel, a maintenance dose of 10 mg is used for patients with acute myocardial infarction, and a maintenance dose of 5 mg is used for those aged \geq 75 years or those weighing <60 kg [6]. For participants in whom clopidogrel will be used, it will be beneficial to proceed with the established standard treatment; it has been reported that subjects using prasugrel have a lower level of drug resistance than the known resistance to the platelet action of clopidogrel due to the pharmacological mechanism. A higher drug effect is expected compared with clopidogrel.

Both clopidogrel and prasugrel may increase the risk of bleeding; however, this is the standard treatment guideline recommended for patients because the risk of treatment complications is not higher than that of the procedure. A retrospective study published in 2018 reported that low-dose prasugrel (5 mg) caused lower ischemic complications than 75 mg clopidogrel (0.9% vs. 6.4%, $P = 0.011$), and hemorrhagic complications were statistically significant. No significant difference was reported (0.5% vs. 2.2%, $P = 0.218$). Therefore, it cannot be concluded that the risk was particularly high in the prasugrel group in this study.

Definition of Adverse Events (AEs)

An AE is defined as any unintended or undesirable sign, symptom, or disease, regardless of whether it is associated with therapy or a drug. AEs will be evaluated from the time of providing informed consent and followed until resolution. An ongoing AE at the last visit will be followed up until the event is resolved or stabilized.

Serious AEs are defined as any event occurring during the study and are considered related to the study.

- ✓ Death
- ✓ Life-threatening condition

- ✓ Permanent or significant disability/incapacity/congenital anomalies/birth defects
- ✓ Result in hospital admission or prolonged hospital stay

In the event of unexpected or unpredictable AEs due to additional procedures and interventions, we considered the best possible treatment so that the study participants could receive appropriate medical treatment. If an adverse event occurs, it will be recorded in the adverse report form attached to the case record, and the principal investigator will report it to the Institutional Review Board Secretariat within 24 h of being recognized.

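### The only stated hypothesis is non-inferiority, but the trial is sized and tested for a difference, with no margin

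*Combined protocol and SAP*

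**What the plan says.** All references are to the combined protocol and SAP.

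- **Specific Aim and Hypothesis.** The one hypothesis is: "we hypothesized that prasugrel has a preventive effect that is not inferior to that of clopidogrel in any treatment group".
- **Determination of the Sample Size.** The calculation presents itself as following from that hypothesis: "Given the hypothesis of the present study, we used a two-proportion Z-test with pooled variance". The error rates come next: "set the significance level at 0.05, power = 0.8". Its inputs are two different event rates: "intraprocedural thromboembolism occurred in the prasugrel group (0.009) and the clopidogrel group (0.064"). The gap between those rates then enters the text in these terms: "with a -0.055 difference in the ratio of any stroke and death during the 30-day treatment". Its result is: "A total of 182 samples were required to prove significance at 80% for each group". Allowing for 10% dropout gives 203 per group, 406 in total.
- **Statistical Analysis.** Binary endpoints, the primary among them, are compared by Pearson's chi-square. "All statistical tests were based on a two-tailed test with a significance level of 5" percent. Efficacy analyses follow intention to treat; no per-protocol analysis is named.
- **Exploratory subgroup analyses.** The list includes "Procedure (stent-assisted coiling, flow-diverter").

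No section gives a non-inferiority margin, a rule based on a confidence limit, or an order for testing non-inferiority and superiority.

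**The concern.** The hypothesis and the design answer different questions. A non-inferiority claim needs a margin fixed in advance and a confidence limit to set against it. A two-tailed chi-square test asks only whether the rates differ.

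If the large planned advantage appears, the mismatch does no harm, because significance in favour of prasugrel also shows non-inferiority at any margin. If prasugrel is moderately better, equal, or about 1.5 times worse, the likely result is P ≥ 0.05. The plan does not say how that result bears on its hypothesis. A reader who goes back to the printed hypothesis could take non-significance as support for it, and that inference would have no valid basis.

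The phrase about any treatment group adds a second ambiguity. If it refers to each type of procedure, the hypothesis covers groups that the plan treats only as exploratory subgroups and does not size for.

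**Working it through.** **Inputs.** From the sample size section: prasugrel 0.009, clopidogrel 0.064, alpha 0.05, power 0.80, 182 evaluable per arm, 10% dropout. From the Statistical Analysis section: two-tailed Pearson chi-square. Assumptions made here: the 6.4% rate, which the plan gives for intraprocedural thromboembolism, is used for the whole primary endpoint; control rates of 4% to 10% serve as a range; margins of 2, 3.2 and 5 points are illustrative, since the plan gives none.

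**1. The plan's own figure.** Pooled two-sided formula, with mean rate p̄ = (0.009 + 0.064)/2 = 0.0365:

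n = [1.96 × √(2 × 0.0365 × 0.9635) + 0.842 × √(0.009 × 0.991 + 0.064 × 0.936)]² / 0.055² = 181.3, so 182 per arm.

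182 / 0.9 = 202.2, so 203 per arm and 406 in total. The plan's numbers reproduce exactly. The sample size section does not state sidedness. The one-sided pooled version gives 143, so two-sided is inferred from the match and from the two-tailed rule in the analysis section. The arithmetic is right, and it is a superiority calculation.

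**2. Chance that the planned test shows prasugrel better, and so also non-inferior.** Exact binomial enumeration of the uncorrected Pearson test, clopidogrel 6.4%:

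| True prasugrel rate | n per arm | Significant in favour of prasugrel |
|---|---|---|
| 0.9% | 182 | 85% (80% by the plan's formula) |
| 0.9% | 203 | 89% |
| 3.2% (half the control rate) | 182 | 29% |
| 6.4% (equal) | 182 | 2% |

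**3. What a non-significant result could hide.** Same method, n = 182, chance that the test does not show prasugrel significantly worse:

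| Control rate | Prasugrel 1.5 times worse | Prasugrel twice as bad |
|---|---|---|
| 4% | 87% (at 6%) | 64% (at 8%) |
| 6.4% | 80% (at 9.6%) | 45% (at 12.8%) |
| 10% | 69% (at 15%) | 23% (at 20%) |

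With equal rates the 95% interval half-width is 1.96 × √(2p(1 − p)/182): 4.0 points at 4%, 5.0 at 6.4% and 6.2 at 10%.

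**4. Non-inferiority power at 182 per arm.** With pP and pC the prasugrel and clopidogrel rates and pC = 0.064, power = Φ[(margin − (pP − pC))/SE − 1.96], where SE = √{[pP(1 − pP) + pC(1 − pC)]/182}. Example, equal rates and a 5-point margin: SE = √(0.119808/182) = 0.02566; 0.05/0.02566 = 1.949; Φ(1.949 − 1.96) = 50%.

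| True prasugrel rate | Margin 2 points | 3.2 points | 5 points |
|---|---|---|---|
| 0.9% | 97% | 99% | >99% |
| 3.2% | 64% | 82% | 96% |
| 6.4% | 12% | 24% | 50% |

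**5. Patients per arm for a non-inferiority design.** 80% power, one-sided 2.5%: n = (1.96 + 0.842)² × [pP(1 − pP) + pC(1 − pC)] / (margin − (pP − pC))². Example, equal rates and a 2-point margin: 7.849 × 0.119808 / 0.0004 = 2351.

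| True prasugrel rate | Margin 2 points | 3.2 points | 5 points |
|---|---|---|---|
| 0.9% | 97 | 72 | 49 |
| 3.2% | 264 | 175 | 107 |
| 6.4% | 2351 | 919 | 377 |

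Steps 4 and 5 use an unpooled normal approximation. At a 0.9% rate that rests on about 1.6 expected prasugrel events (182 × 0.009), so the first row of each table is rough.

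**The case against.** The strongest reply is that one sentence is loosely worded and the rest of the plan points to superiority. The background cites a significantly lower event rate with prasugrel, the sample size rests on that difference, the test is two-tailed, and the Possible Risks and Benefits section expects prasugrel to have the greater effect. Nothing commits the sponsor to reading a non-significant result as non-inferiority, and the recommended fix leaves the primary P value unchanged.

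Much of this is fair. Superiority was probably intended, and the harm lies in interpretation, not in a miscalculated analysis. But an expectation voiced in the risk and benefit text is not a hypothesis, and the sample size section ties itself to the one hypothesis that is stated. That hypothesis still has no decision rule.

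Three narrower points also stand:

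- A non-significant result is the likely one when prasugrel is about 1.5 times worse. At twice the 6.4% rate, a significantly worse result is slightly more likely (55%).
- The 29% figure partly reflects an optimistic planned effect, a problem that rewording would not remove. It bears on this point because it shows that a non-significant result is a realistic prospect.
- A non-inferiority design is expensive mainly when no benefit is assumed. At 3.2% versus 6.4%, margins of 3.2 and 5 points need 175 and 107 per arm, within the planned 182.

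**Conclusion.** The concern holds and must be fixed. The plan's only hypothesis is non-inferiority, while its sample size and tests address a difference, and there is no margin or confidence-interval rule to connect them. The sample size of 182, then 203 per arm, is correct for superiority.

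The gap has no effect if prasugrel proves significantly better. In every other outcome the plan gives no valid route to its stated conclusion. How often that happens depends on the true effect: about 15% of the time at the planned rates (100 − 85), and about 71% if prasugrel halves the event rate (100 − 29). Whether the data could then support non-inferiority turns on the missing margin: at equal rates, power runs from 12% to 50% over margins of 2 to 5 points.

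These sizes assume 182 evaluable per arm, a 6.4% control rate for the whole primary endpoint, and illustrative margins. The mismatch itself depends on none of them.

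**What to change.** Before any unblinded outcome data are seen, and with the change documented:

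1. Restate the hypothesis as superiority: prasugrel reduces the primary endpoint compared with clopidogrel, at two-sided alpha 0.05.
2. Clarify or remove the reference to any treatment group.
3. State that a non-significant result will not be interpreted as non-inferiority or equivalence.
4. Report the risk difference with a score-type 95% confidence interval for the primary endpoint and, as a reporting addition, for bleeding.

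This costs a few sentences and some extra intervals. The design, primary test and 406 patients do not change. What the sponsor gives up is an informal non-inferiority claim.

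If non-inferiority is to be kept, the plan needs a justified margin, a decision rule on the upper limit of the two-sided 95% confidence interval for the risk difference (prasugrel minus clopidogrel), both intention-to-treat and per-protocol analyses, and a recalculated sample size. The requirement could fall below the present 182 per arm or rise above 2000, depending on the margin and on whether a true benefit is assumed.

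### Randomisation has no stated day and may come well before first dose, while the clinical endpoints start at the procedure and non-adherent patients are removed after allocation, so the intention-to-treat analysis is undefined for patients lost before Day 0

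*Combined protocol and SAP*

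**What the plan says.** All references are to the combined protocol and SAP.

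- **Research Design, steps 2 to 4.** Step 2 is angiography and consent: "detailed consent was obtained after the study protocol was explained to the participants who met the selection criteria". Step 3 is allocation: "Using a randomization program, the test group (203 patients; aspirin 100 mg + prasugrel 5 mg) and the control group". Step 4 is prescription: "The above drugs were prescribed according to the assigned group and taken 5 days before the procedure". No step gives a day for allocation.
- **Time table.** Consent and eligibility are marked only under screening, Day -60 to -6. There is no randomisation row. The Day -5 outpatient column shows no assessments, and eligibility is not marked at any later visit.
- **Step 5, at admission on Day -2.** Drug intake is checked, and "if the drug was not taken properly, the patient was excluded from the study".
- **Study Endpoints.** The primary endpoint has two parts: "A thromboembolism detected during the neurointerventional procedure" and "Transient ischemic attack, ischemic stroke, or death with evidence of infarction on diffusion-weighted imaging, occurring within 30 days after the procedure". The four listed secondary endpoints are strokes within 30 days after the procedure or a lesion on the postprocedural MRI. One more precedes the procedure: "Another secondary endpoint was the preprocedural platelet function test value and its adjustment ratio".
- **Statistical Analysis.** "All the efficacy analyses were based on the intention-to-treat principle". No analysis set is defined. The only remark on missing values concerns safety.
- **Randomization.** A third party manages the program so that researchers are blinded. Steps 4, 6 and 8 nevertheless prescribe by assigned group, and step 6 adjusts treatment by an arm-specific scheme. No placebo or masking of study drug is described.

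**The concern.** Intention to treat needs an outcome, or a stated counting rule, for everyone allocated. Here patients can be lost between allocation and Day 0 in several ways. They may withdraw, start an excluded drug, be re-planned to a treatment without a stent or flow diverter, have an event, or be excluded at step 5. The plan covers only the last of these, and its instruction there is to remove the patient.

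Three things are at stake.

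1. **Selective loss.** Whoever prescribes can see the arm, so a decision to cancel, re-plan or judge intake improper may depend on it. Adherence itself may also differ by drug.
2. **Uncounted events.** A stroke, TIA or death on assigned drug before Day 0 falls outside both primary components.
3. **An open choice.** Whether untreated patients are dropped, kept as non-events or treated as missing could be settled after the data are seen.

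**Working it through.** **1. Interval from allocation to first dose.** Inputs: screening from Day -60 to -6 and pre-medication on Day -5 (Time table).

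- Longest: -5 - (-60) = 55 days, or 56 with the one-day visit window.
- Shortest from the screening window: -5 - (-6) = 1 day.
- Steps 3 and 4 are also consistent with allocation at the Day -5 contact itself.

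The documents therefore permit about 55 days but do not prescribe it.

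**2. The plan's sample size.** Inputs (Determination of the Sample Size; two-sided test from Statistical Analysis): p1 = 0.009, p2 = 0.064, d = 0.055, alpha 0.05, power 0.80, pooled Z-test. The mean rate is 0.0365.

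n = [1.960 × √(2 × 0.0365 × 0.9635) + 0.842 × √(0.009 × 0.991 + 0.064 × 0.936)]² / 0.055²
= [1.960 × 0.2652 + 0.842 × 0.2623]² / 0.003025 = 181.3, so **182** per arm.

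With 10% dropout, 182 / 0.9 = 202.2, so **203**. Both of the plan's figures reproduce.

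**3. Effect on power of patients without a procedure.** Power = Φ[(d√n - 1.960 × √(2p̄q̄)) / √(p1q1 + p2q2)]. The untreated share f is an assumption; the only related figure in the plan is the 10% dropout.

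| f in each arm | left out of analysis | kept as non-events (n = 203) |
|---|---|---|
| 0 | 84.3% | 84.3% |
| 5% | 82.4% | 82.3% |
| 10% | 80.3% | 80.1% |
| 20% | 75.5% | 75.1% |

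At f = 10% with non-event coding, the rates become 0.81% and 5.76%, so the difference shrinks from 5.5 to 4.95 percentage points. Counting those same patients as events would give 31.1%. Exclusion and non-event coding thus cost little power up to 10%, but the three possible codings are far from equivalent.

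**4. Sensitivity to a few events.** Expected primary events per arm: 203 × 0.009 = 1.8 and 203 × 0.064 = 13.0. Pearson chi-square without correction, 203 per arm:

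| prasugrel events | clopidogrel events | p |
|---|---|---|
| 2 | 13 | 0.004 |
| 3 | 13 | 0.011 |
| 4 | 13 | 0.026 |
| 5 | 13 | 0.054 |

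Three prasugrel-arm events that occurred but were not counted would decide significance.

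**5. Loss unrelated to outcome.** A 10% loss is about 20 patients per arm, carrying 20.3 × 0.009 = 0.2 and 20.3 × 0.064 = 1.3 expected events. Random loss of this size changes little. Loss related to outcome or arm, and real events left uncounted, are what matter.

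**6. Step 5 against the analysis statement.** Step 5 acts at Day -2, after allocation at step 3. Excluding those patients from the study and analysing all randomised patients cannot both be done.

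**The case against.** The following can fairly be said on the other side.

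- **The gap may not exist in practice.** Steps 3 and 4 run directly from allocation to prescription, and there is a Day -5 outpatient contact. This stands in part. A reader might infer that patients are randomised 55 days ahead; the documents support only that this is allowed and that the day is unstated. The step 5 conflict and the missing counting rule hold whatever the day.
- **Not every efficacy endpoint depends on the procedure.** Correct. The platelet function value and its adjustment ratio are obtained on Day -1, so the point is limited to the primary endpoint and the four listed stroke and MRI endpoints.
- **Untreated patients could be kept as non-events.** Correct. It is tempting to say that they cannot have an outcome, but what is missing is a rule, not the possibility of one.
- **The dropout allowance covers the loss.** It does for power, as shown above. It does nothing for selective loss.
- **Researchers are said to be blinded.** That statement describes who manages the randomisation program. It is hard to reconcile with prescribing and adjusting treatment by arm with no masking of drug described.
- **Dilution is conservative.** For the two-sided difference test that was sized, it is. The stated hypothesis, however, is that prasugrel is not inferior, and under that reading dilution is favourable.
- **The aim is periprocedural, so starting at Day 0 is legitimate.** This stands. Starting the primary clock at first dose would change the estimand, so it belongs in a sensitivity analysis.

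**Conclusion.** The point holds in a limited form. The plan allows allocation well before first dose without a later eligibility check, and it gives randomised patients who never have the procedure no defined outcome on the primary or the listed stroke and MRI endpoints. It leaves events between Day -5 and Day 0 uncounted, and it excludes patients after randomisation while claiming intention to treat.

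A reader might infer that the trial is too small. The documents do not support that: 182 and 203 per arm reproduce, and 10% loss leaves about 80% power.

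The issue is possible bias. Its size cannot be estimated, because the documents give no rate of cancellation, non-adherence or events before Day 0. The illustration of three further prasugrel events moving p from 0.004 to 0.054 rests on the planning rates and on all 203 patients per arm being in the denominator; it is not a forecast. That loss may differ by arm rests on reading the arm-specific prescribing as visible to those who manage the patient.

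**What to change.** 1. **Timing.** Run the randomisation program at the Day -5 outpatient contact, after re-confirming eligibility and the planned stent or flow-diverter procedure. Add randomisation and that check to the time table.
2. **Analysis set.** Define the primary set as all randomised patients in their assigned arms. Reconcile step 5 with it: improper intake is recorded, but the patient stays in the analysis and in follow-up.
3. **Counting rule.** State before unblinded data are reviewed how a patient without a procedure counts in the primary endpoint. Non-event with the full denominator is one workable rule. Report the number of such patients and the reasons by arm, and collect their Day 30 status.
4. **Sensitivity analysis.** Count stroke, TIA and death from first dose to 30 days after the procedure, or to 35 days after first dose (5 + 30) if none is done. Leave the primary clock at the procedure.

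**Cost.** Changes to the time table, step 5 and the analysis text, with no extra visit for treated patients. Allocation is known later, so drug must be dispensed at a Day -5 contact that currently has no assessments. The few untreated patients need a Day 30 contact. Because the second primary component refers to diffusion-weighted imaging, a contact alone may not settle a suspected event in them, and the rule should say what evidence is accepted.
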